2.3.2 Secondary Variables

- Change of CAS between the observation timepoints and the baseline: comparison between the treatment groups
- Comparison of frequency of adverse events between NR-RTX and R-GC.
- TRAb antibodies

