Does RTX lower the CAS of the non-steroid responsive TAO-patients (NR-RTX), in comparison to NR-C, that continued with iv GC, and R-GC? Do the background variables differ between NR-RTX and NR-GC or R-GC? And lastly, does the QoL differ between the R-GC and the NR-RTX at given measuring points?

Material and Methods

Study design

The RTX-study is a non-randomized prospective study that covers patients with moderate-severe TAO with indication for treatment with iv GC. For this study, a control group (NR-C) will be created.

Patients with TAO are evaluated at Department of Ophthalmology at Sahlgrenska University Hospital/ Mölndal's and are asked for participation if eligible. Variables collected at each visit Clinical Activity Score (CAS), Quality of Life (QoL) through ThyPRO self-assessment questionnaire, biochemical tests (fT4, fT3, TSH, TRAb, liver function tests, fasting blood glucose), blood pressure and waist. An oral glucose tolerance test (OGTT) is performed at 12, 18, and 46 weeks, and a short adrenocorticotrophic hormone (ACTH) test at 12 and 46 weeks. Dual-energy x-ray absorptiometry (DXA) of the spine is conducted at 0 and 18 weeks.

All patients in the RTX-study start the 12-week scheme of iv GC at baseline. After four weeks of treatment, an evaluation of the treatment outcome is made. If the patients have improved their CAS score by ≥ 2 points, they are classified as responders to iv GC (R-GC) and continue their 12-week iv GC scheme. The remainder of the patients are classified as non-responders to the treatment with iv GC and are switched to 1000 mg iv RTX in week 5 and 7, combined with a weekly oral dose of 12.5 – 15 mg MTX (NR-RTX). The RTX is administered at the department of Rheumatology at Sahlgrenska University Hospital. All included patients have thereafter follow-up visits at week 12, 18, 32, 46 and 68 weeks after baseline.

At week 18 and at all follow-up timepoints thereafter, patients in R-GC group are evaluated for possible relapse. If a patient in R-GC has a CAS ≥ 4 points and CAS has worsened by ≥ 2 points compared to the value measured in the prior evaluation time-point, the patient is

considered having a relapse. Patients with relapse are randomized to either treatment with RTX and MTX or with *per oral* GC and MTX.

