All patients included in the study are assessed according to study protocol, but if DON is developed, the affected patient is treated outside the study protocol in order to follow DON treatment regimen. The patients with DON still have the same evaluation time points as the other patients in the study, but they are excluded from the comparisons between groups after the occurrence of DON.

From the group of patients with moderate – severe TAO with indication for treatment with iv GC that do not meet inclusion/exclusion criteria for the RTX-study or declined participation, a control group (NR-C) of non-responders will be created. As they are not included in the RTX study, they continue with their 12 weeks scheme of iv GC treatment.

Data collected at the follow-up timepoints: QoL, safety data and information on adverse events.

Study population

Inclusion criteria for the RTX study: man or woman between 18-70 years old, TAO with 7-point score system of CAS ≥ 4 (less than 3 months old), euthyroid for at least 6 weeks.

Exclusion criteria for the RTX study were: DON, ulcerative corneal involvement, previous treatment with steroids for TAO (except for prophylaxis for TAO in connection with RAI), previous treatment with RTX, positive Hepatitis B or C serology, obtained a living vaccine within 4 weeks prior RTX+MTX to evaluation, history of recurrent significant infection or history of recurrent bacterial infections, assessment by the investigator that the patient may not attend to the protocol, current pregnancy or lactation, significant cardiac disease, including significant or uncontrolled arrhythmia, previous active tuberculosis, bone marrow depression with leukopenia, thrombocytopenia or significant anaemia, allergy to the active substance or any other substance in the medications or murine proteins, active, severe infections (such as tuberculosis, sepsis or opportunistic infections), patients with severe immunosuppression, severe cardiac failure or severe uncontrolled heart disease.

The TAO patients not included in the RTX-study will be identified using the diagnosis-related group (DRG) registry according to the 10th revision (ICD-10) in VGR. In DRG, a combination of different codes was used (TAO [H06.2], Graves' disease [E05.0] and iv infusion [DT016]).

Efficacy variables

In the study, both patients' eyes are evaluated regarding CAS and the score of and any improvement of the worst eye was used.

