2.2 Variables evaluated throughout the study

- TRAb antibodies
- Waist circumference change (%)

- High systolic blood pressure (ja/nej)
- High diastolic blood pressure (ja/nej)
- ALT increased (ja/nej)
- AST increased (ja/nej)
- OGTT results (diabetes/glucose intolerance)
- Short ACTH test (normal/inadequate response)
- Collected information on patient-reported adverse events

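### The adverse-event comparison of NR-RTX with R-GC has no onset window or attribution rule, so events from the shared iv GC weeks 0-4 may be counted in both groups.

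*SAP*

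**What the plan says.** SAP section 2.3.2 plans "Comparison of frequency of adverse events between NR-RTX and R-GC". It gives no onset window, no unit (patients or events) and no attribution rule. SAP section 3 adds only general tests, of which Fisher's exact test would apply to a yes/no event variable. The one cut-off stated for group comparisons, in the protocol's study design text, concerns patients who develop DON.

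The sequence of treatment is in the protocol under Study design:

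- Shared start: "All patients in the RTX-study start the 12-week scheme of iv GC at baseline".
- Separation into groups: "After four weeks of treatment, an evaluation of the treatment outcome is made".
- Non-responders are then "switched to 1000 mg iv RTX in week 5 and 7", together with weekly MTX. Responders continue iv GC.
- Place of infusion: "The RTX is administered at the department of Rheumatology at Sahlgrenska University Hospital".
- Later visits: "All included patients have thereafter follow-up visits at week 12, 18, 32, 46 and 68 weeks after baseline".
- From week 18, R-GC patients who relapse are randomized to RTX plus MTX or to oral GC plus MTX.

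On data collection, the protocol says "Data collected at the follow-up timepoints: QoL, safety data and information on adverse events". SAP section 2.2 lists "Collected information on patient-reported adverse events" among the variables evaluated throughout the study. Adverse events are not in the protocol's list of variables collected at each visit.

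**The concern.** During weeks 0-4 the labels NR-RTX and R-GC do not yet exist, and every patient is on the same drug. A by-group count that starts at baseline puts steroid events that precede any RTX under the NR-RTX label, and the same kind of event under R-GC. Those events carry no information on RTX against continued iv GC. They blur the contrast and, if early tolerance of iv GC is related to response, they bias it.

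There is a mirror problem later on. An R-GC patient randomized to RTX plus MTX at relapse can have events on RTX that stay under R-GC, because no rule says otherwise.

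The third issue is data capture. The infusions fall in weeks 5 and 7, and the next listed visit is week 12. If patients are first asked at that visit, short-lived events around the infusions may be missed or misdated, and without onset dates they cannot be separated from events on iv GC.

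The Background section of the protocol motivates RTX partly by the side effects of high-dose steroids, and this is the only adverse-event comparison between groups in the SAP.

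**Working it through.** **There is no planned figure to reproduce.** SAP section 1.4 states that no power calculation was done, and neither document gives group sizes or event rates. The schedule arithmetic below uses document figures. The rates, the group size and independence are assumptions.

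**Schedule (protocol, Study design).**

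- Shared phase as a share of the time to the first follow-up visit: 4/12 = 33%. As a share of the whole study: 4/68 = 5.9%.
- Gap from infusion to the week-12 visit: 12 - 5 = 7 weeks and 12 - 7 = 5 weeks.

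**Dilution when early rates are equal.** Read frequency as the proportion of patients with at least one event. Let p0 be the probability of an event in weeks 0-4, the same in both groups and independent of later events. Let q be the probability of an event after week 4. Then

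P(any event) = 1 - (1 - p0)(1 - q),

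and the difference between groups is (1 - p0)(q1 - q2). The factor (1 - p0) depends neither on group size nor on which group has the higher rate.

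The table uses assumed later rates of 30% and 70%. Power is for a two-sided Fisher exact test at 0.05, enumerated exactly for an assumed 25 patients per group.

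| p0 | Lower group | Higher group | Difference (points) | Power |
|---|---|---|---|---|
| 0 | 30% | 70% | 40 | 78% |
| 10% | 1 - 0.9 × 0.7 = 37% | 1 - 0.9 × 0.3 = 73% | 36 | 68% |
| 20% | 1 - 0.8 × 0.7 = 44% | 1 - 0.8 × 0.3 = 76% | 32 | 57% |
| 40% | 1 - 0.6 × 0.7 = 58% | 1 - 0.6 × 0.3 = 82% | 24 | 34% |

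With later rates of 30% and 60%, power is 51% at p0 = 0, 33% at 20% and 19% at 40%.

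A smaller assumed contrast, 20% against 40%, shows the same pattern. The 20-point difference becomes 18 at p0 = 10%, 14 at 30% and 10 at 50%.

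**Spurious difference when early rates differ.** Suppose later rates are truly equal at 30%, with early rates of 40% in NR-RTX and 20% in R-GC:

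- NR-RTX: 1 - 0.7 × 0.6 = 58%
- R-GC: 1 - 0.7 × 0.8 = 44%

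This gives 14 points against NR-RTX where there is no later difference. With the early rates reversed, it is 14 points in its favour.

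**The case against.** A reader might infer that the plan charges steroid events to NR-RTX. The documents do not say so. Any weeks 0-4 events that are counted enter R-GC as well, so with equal early rates the effect is symmetric dilution. A one-sided distortion needs early rates that differ by response status, and the documents give no information on that.

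A reader might also infer that infusion events rest on recall at week 12. That is a natural reading of the visit schedule, but it is not stated. The protocol sentence on data at follow-up comes directly after the paragraph on the NR-C controls, so its scope is unclear. SAP section 2.2 is headed as covering the whole study. Recording at the week-4 evaluation or in the infusion department is neither described nor excluded. What stands is that no such collection point is explicitly described.

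Nor can it be said that the comparison is unable to answer its question. The shared phase is 4 of 68 weeks. Reports covering the intervals after week 12 would not contain it; only the first report is mixed.

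Safety is not among the protocol's three aims or SAP objectives A and B, and this is one secondary variable in a non-randomized study. The size of the effect depends wholly on assumed inputs: at p0 = 10% the loss is modest, and 40% is a high value for four weeks. These points limit how much weight the concern can carry. They do not supply the missing window or attribution rule.

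**Conclusion.** The concern holds in limited form. SAP section 2.3.2 compares adverse-event frequency by groups that are formed only at week 4, with no rule on onset or attribution. Events from the identical first four weeks may therefore be counted in both groups. With equal early rates, the difference in the any-event proportion shrinks by (1 - p0), so that an assumed 40 points becomes 36, 32 or 24 at p0 of 10%, 20% or 40%. With unequal early rates, a false difference can appear in either direction. The result is a comparison that is diluted and hard to attribute, not an uninterpretable one.

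The shrinkage factor rests on equal early rates, on independence of early and later events, and on reading frequency as the proportion of patients with any event. The power figures also rest on the assumed later rates and 25 patients per group. The missing rule for relapsed R-GC patients follows from the documents alone. So does the absence of a described collection point between the infusions and week 12, but whether events are in fact captured there cannot be settled from the text. The change should be made: it is cheap and it concerns the only planned adverse-event contrast.

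**What to change.** In SAP section 2.3.2:

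- Define the main comparison as the proportion of patients with at least one adverse event with onset after the week-4 classification, with the same start point in both groups. Starting NR-RTX at its first RTX or MTX dose but R-GC at week 4 would count the interval in between for R-GC only.
- Tabulate events with onset in weeks 0-4 separately, for all patients pooled, as events on iv GC.
- For R-GC patients randomized at relapse, end the count at the start of relapse treatment, and report later events by treatment received.

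In the protocol, state that adverse events are recorded with onset date, using the same prompts in both groups, at the existing week-4 evaluation and at the existing infusion attendances (RTX for NR-RTX, iv GC for R-GC), as well as at the follow-up visits.

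The cost is a few lines of SAP and protocol text and an onset date for each event, collected at attendances that already take place. No visit or treatment changes. The small downside is that fewer events enter the main comparison.

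### The only adverse-event comparison is one undivided frequency, which can dilute or hide an excess of infection or infusion reactions under RTX+MTX

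*SAP*

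**What the plan says.** SAP 2.3.2 lists one adverse-event analysis among the secondary variables: "Comparison of frequency of adverse events between NR-RTX and R-GC". It does not say whether patients or events are counted, over what period, or by what type or seriousness. SAP 3 adds only generic tests, with Fisher's exact test for dichotomous variables.

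SAP 2.2 lists the variables followed through the study. The safety-related ones are "Waist circumference change", "High systolic blood pressure (ja/nej") and its diastolic counterpart, "ALT increased (ja/nej") and the same for AST, the OGTT result, the short ACTH test, and "Collected information on patient-reported adverse events". The Protocol (Study design) gives the visit schedule as CAS, QoL, "biochemical tests (fT4, fT3, TSH, TRAb, liver function tests, fasting blood glucose), blood pressure and waist", with OGTT, ACTH test and spinal DXA at set weeks. No blood count is listed. The same section ends by saying that safety data and adverse-event information are collected at follow-up, without defining the safety data.

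On exposure, the Protocol (Study design) starts every patient on the 12-week iv GC scheme. Responders at week 4 continue it (R-GC). Non-responders are switched to RTX in weeks 5 and 7 with weekly oral MTX (NR-RTX). From week 18, R-GC patients who relapse are randomized to RTX+MTX or to oral GC+MTX.

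**The concern.** The two groups are exposed to different drugs with different expected harms. R-GC has the longer iv GC course, so it may show more steroid-type events. NR-RTX alone receives RTX+MTX in the main phase, so it may show more infection or infusion-type events. When two differences can run in opposite directions, a single total is a poor summary: each works against the other.

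The separately listed variables do not make up for this. Waist, blood pressure, OGTT and ACTH (and DXA and fasting glucose in the Protocol) fit steroid effects. Only ALT/AST could reflect MTX, and they are not specific to it. An excess of infection or infusion reactions would have to show itself in the adverse-event line.

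At stake is how the safety result will be read. The Protocol's Background cites earlier reports of fewer side effects with RTX. A finding of similar adverse-event frequency could be taken as support for that while a clinically important excess of one kind sat inside the total.

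**Working it through.** The plan gives no event rate, group size, alpha or power (SAP 1.4 states that no power calculation was made), so there is no figure of its own to reproduce. What follows is an illustration.

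**Inputs, all assumed**
- Group sizes, NR-RTX v R-GC: 15 v 30, with other sizes below.
- Two-sided alpha 0.05.
- Counting unit: patients with at least one event.
- RTX/MTX-type risk (infection and infusion reactions together): 40% v 10%.
- Steroid-type risk: three scenarios.
- The two types occur independently within a patient.

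**Formula.** Risk of any event = 1 − (1 − RTX/MTX-type risk) × (1 − steroid-type risk). Power is for Fisher's exact test (SAP 3), summed over all binomial outcomes.

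**Any-event risks**
- Offsetting steroid difference, 35% v 60%: 1 − 0.60 × 0.65 = 61% v 1 − 0.90 × 0.40 = 64%.
- Partial offset, 40% v 45%: 1 − 0.60 × 0.60 = 64% v 1 − 0.90 × 0.55 = 50.5%.
- No steroid difference, 20% v 20%: 1 − 0.60 × 0.80 = 52% v 1 − 0.90 × 0.80 = 28%.

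**Power at 15 v 30**

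| Steroid-type scenario | Any event | Pooled | RTX/MTX-type class alone |
|---|---|---|---|
| Offsetting | 61% v 64% | 3.7% | 59% |
| Partial offset | 64% v 50.5% | 8.9% | 59% |
| No difference | 52% v 28% | 29.6% | 59% |

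**Other sizes.** In the offsetting scenario, pooled power is 3.5% at 10 v 20 and 4.3% at 20 v 40. Power on the class alone is 42% and 72%.

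**Smaller risks.** With RTX/MTX-type 30% v 10% and steroid-type 20% v 40%, any event is 1 − 0.70 × 0.80 = 44% v 1 − 0.90 × 0.60 = 46%. Power at 15 v 30 is 3.0% pooled and 34% by class.

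The pooled frequency has less power than the class in every scenario tried. It loses the signal almost entirely only where the steroid difference is about as large as the RTX/MTX difference; otherwise it dilutes it.

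**The case against.** The strongest reply is that this is under-specification and no more. SAP 2.3.2 never says overall or any event, and a frequency per event type would fit the same words. That is fair: pooling is the natural reading of a line that names no categories, but not the only one. The line still fixes no classes, and classes chosen after the events are seen are open to selection.

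A reader might infer that RTX/MTX harms can reach the data only through patients' own reports. The documents do not support that, since the Protocol also collects safety data at follow-up. That term is undefined, however, and no SAP analysis uses it.

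A reader might also take the exclusion criteria, such as "history of recurrent significant infection or history of recurrent bacterial infections" and "bone marrow depression with leukopenia, thrombocytopenia or significant anaemia, allergy to the active substance", as the sponsor's list of harms feared from RTX/MTX. The Protocol does not say so. They apply to every patient before iv GC starts and stand beside criteria unrelated to drug harm, so this point does not rest on them.

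The measured steroid effects are separate variables in SAP 2.2 and are not said to enter the adverse-event frequency. An offset therefore needs steroid-type complaints among the reported events themselves, at rates the documents do not give. This stands, and it limits how much cancellation can be claimed.

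Splitting does not rescue a rare harm. If serious infection were 20% v 5% (assumed), Fisher power at 15 v 30 would be only 30%. This favours estimates with intervals over more tests. Finally, safety is in no stated aim, and the groups are non-randomized responders and non-responders, so no tabulation will make the comparison causal.

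**Conclusion.** The concern holds in a limited form. As written, the adverse-event comparison has no class, seriousness, unit or period. Under the natural reading it can dilute, and with opposite differences of similar size can hide, an excess of infection or infusion reactions in NR-RTX. The other scheduled safety variables would not show that excess.

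It would go too far to conclude that the differences will cancel. Near-complete loss of signal depends on nearly equal opposite differences. In the illustration, pooled power at 15 v 30 runs from about 4% to 30%, against 59% for the class alone. Every risk and group size behind those figures is assumed, as are independence and alpha. The direction of the problem follows from the design; its size cannot be derived from the documents. The SAP should be changed, but this is a secondary variable and the point does not touch the CAS analysis.

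**What to change.** In SAP 2.3.2, replace the single frequency by the number of patients with at least one event in pre-defined classes: steroid-type, infection, infusion or allergic reaction, hepatic, and other. Add serious events. Give each as a risk difference with a 95% CI.

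- **Sources.** Classify the adverse events and safety data the Protocol already collects, using the same sources in both groups.
- **Infusion reactions.** Report these descriptively. Reactions to RTX can arise only in patients given it and would be recorded at Rheumatology, where it is infused, so ascertainment is not comparable between groups.
- **Cytopenia.** Do not add a between-group comparison. No blood count is scheduled, so detection would depend on unscheduled testing that may differ by group.
- **Period.** Report events before and after the week-4 evaluation separately, because until then both groups are on iv GC. Report R-GC events after relapse re-treatment separately, because those patients may then be receiving RTX+MTX or oral GC+MTX.

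The cost is SAP wording and some event-coding work, plus a few more comparisons, which are reported as estimates. It needs no new patients, visits or laboratory tests and leaves treatment unchanged.

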3 STATISTICAL METHODOLOGY

Tests between groups will be made for the NR-RTX group and all of the other groups one at a time; R-GC and NR-C (where applicable).

For continuous variables Mann-Whitney U-test will be used for analyses between two groups. For dichotomous variables Fisher exact test will be used for test between two groups. For ordered categorical variables Mantel Haenszel Chi Square test will be used for test between two groups.

For all continuous variables Wilcoxon's Signed-Rank test will be used for within group analyses.

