PROTOCOL

TITLE. Rituximab (RTX) Therapy in Patients With Active TAO

NCT 02378298

Date 2011-08-24

Background

Every year, 2000 patients in Sweden get the diagnosis of a diffuse autoimmune hyperthyroidism (Grave's disease (GD)). About 40% of the patients with GD have some complaints from their eyes indicating thyroid associated ophthalmopathy (TAO) in its mild form. Moderate-severe forms are seen in approximately 5-10% of GD patients. TAO is an autoimmune complication of GD and the inflammation causes swelling of the periorbital fat, muscles and connective tissue. The patient obtains symptoms such as red eyes, pain, epiphora, diplopia and sometimes exophthalmos. This affects the patient's quality of life (QoL) negatively.

Today, the primary treatment of moderate-severe TAO is high doses of intravenous (iv) steroids, with the purpose to suppress the inflammation. High doses of iv steroids cause side effects, therefore, it is motivated only in moderate-severe cases. Even when the treatment is given early in the course of the disease, only 70-80% of the patients respond to the treatment (responders). The treatment effect on the inflammation is most commonly measured with Clinical Activity Score (CAS) – a score recommended by the European Group of Graves orbitopathy (EUGOGO).

Ten years ago, small observational studies reported promising result on Rituximab (RTX) treatment in TAO, given less side-effects. RTX is an immunomodulating drug where antibodies affect B-cells.

Objectives

The primary aim of this study is to evaluate the effect of Rituximab (RTX) in Thyroid Associated Ophthalmopathy (TAO) patients who are non-responsive to treatment with iv GC (NR-RTX), with patients controls that continued with iv GC even though they did not respond (NR-C). A second aim is to compare the NR-RTX patients with the steroid responsive ones (R-GC) and NR-C, regarding background variables (gender, age, smoking status, duration of GD, duration of eye symptoms, thyroid treatment and lab) and efficacy variables (CAS, CAS SU/M, severity, proptosis and subjective diplopia). Lastly, a third aim is to evaluate and compare the QoL between the R-GC and the NR-RTX in the study at given time points.

Research questions

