1.4 Power Calculation

No power calculation was performed due to the lack of data from any similar study of RTX in GC non-responders

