2.3 Analysis Variables

2.3.1 Primary Variable

- Change of CAS (clinical activity score) between the observation timepoints and the previous timepoint: comparison between the treatment groups
- CAS: comparison between the treatment groups at the different timepoints

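### SAP section 3 plans tests but no effect estimates or confidence intervals, and there is no power calculation, so a non-significant CAS or adverse-event comparison could not be told apart from an imprecise one

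*SAP*

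**What the plan says.** SAP section 3 assigns one procedure to each type of variable:

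- Continuous, between groups: "For continuous variables Mann-Whitney U-test will be used for analyses between two groups".
- Dichotomous: "For dichotomous variables Fisher exact test will be used for test between two groups".
- Ordered categorical: "For ordered categorical variables Mantel Haenszel Chi Square test will be used for test between two groups".
- Within groups: "For all continuous variables Wilcoxon's Signed-Rank test will be used for within group analyses".

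NR-RTX is tested against R-GC and NR-C one at a time. The two primary variables in section 2.3.1 are "Change of CAS (clinical activity score) between the observation timepoints and the previous timepoint: comparison between the treatment groups" and "CAS: comparison between the treatment groups at the different timepoints". Section 2.3.2 adds change from baseline and a comparison of adverse-event frequency between NR-RTX and R-GC.

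On size, section 1.4 says: "No power calculation was performed due to the lack of data from any similar study of RTX in GC non-responders". Neither document gives a target number of patients, a detectable difference, a CAS standard deviation or a significance level.

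**The concern.** The protocol's primary aim (Objectives) is to evaluate what RTX does in steroid non-responders compared with non-responders who stayed on iv GC. That is a question about size. A Mann-Whitney or Fisher p-value does not answer it, because it mixes the size of the difference with the number of patients. A study with a power calculation has at least stated in advance which difference a negative result speaks against. This one has not, so an interval would be the only planned guide to what a non-significant result leaves open, and none is planned.

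At stake is the reading of a p-value above whatever threshold is used. For CAS, a real benefit could be written up as none. For adverse events, a non-significant Fisher test could be taken as similar safety when the data allow a large difference.

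**Working it through.** **Is an estimate planned anywhere?** SAP section 3 names four procedures, all of them tests. Section 2.3 names variables and comparisons but no effect measure. The protocol adds neither an estimate nor an interval. With no stated sample size or power, there is no figure of the plan's own to reproduce.

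**Inputs for the illustration (all assumed).** Equal groups of 5 to 100, CAS SD 1.0 to 2.0, two-sided 5% level, true differences of 1 or 2 points. The only input from the documents is the 7-point CAS scale (protocol, Study population).

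**Precision.** Half-width = t(0.975, 2n−2) × SD × √(2/n). With equal sizes and equal observed SDs, the Welch interval is identical. For n = 10 and SD 1.5: 2.101 × 1.5 × √0.2 = 1.41 points.

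| n per group | SD 1.0 | SD 1.5 | SD 2.0 |
|---|---|---|---|
| 5 | 1.46 | 2.19 | 2.92 |
| 8 | 1.07 | 1.61 | 2.14 |
| 10 | 0.94 | 1.41 | 1.88 |
| 20 | 0.64 | 0.96 | 1.28 |
| 30 | 0.52 | 0.78 | 1.03 |

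**Power of the planned test.** Mann-Whitney on simulated normal scores, rounded and limited to 0–7, control mean 4, 3,000 runs per cell:

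| n per group | 1 point, SD 1.5 | 1 point, SD 2.0 | 2 points, SD 1.5 | 2 points, SD 2.0 |
|---|---|---|---|---|
| 5 | 12% | 7% | 35% | 21% |
| 8 | 20% | 14% | 63% | 40% |
| 10 | 25% | 17% | 76% | 51% |
| 20 | 49% | 32% | 98% | 84% |
| 30 | 68% | 45% | >99% | 96% |

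Power runs from 7% to nearly 100%, and the documents do not say where in this range the study lies.

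**The same p-value, two meanings.** Take a t-test p of 0.20 with SD 1.5, counting benefit as control minus NR-RTX.

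- 8 per group: SE = 1.5 × √(2/8) = 0.75; difference = 1.345 × 0.75 = 1.01; 95% CI = 1.01 ± 2.145 × 0.75 = −0.60 to 2.62.
- 100 per group: SE = 1.5 × √(2/100) = 0.212; difference = 1.286 × 0.212 = 0.27; 95% CI = 0.27 ± 1.972 × 0.212 = −0.15 to 0.69.

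The first interval leaves a 2-point benefit open; the second excludes even a 1-point benefit. The p-value is the same.

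**Adverse events (assumed counts).** With 0 events in 10 patients, the exact two-sided 95% upper limit is 1 − 0.025^(1/10) = 30.8%. With 0/10 against 4/10, the probability that all four events fall in one named group is C(10,4)/C(20,4) = 210/4845 = 0.0433; doubling gives a Fisher p of 0.087. An observed gap of 40 percentage points would be non-significant.

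**The case against.** Four objections have weight.

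- **The missing power calculation is disclosed and explained.** This stands: section 1.4 gives a reason, and the omission is not in itself the error. But an interval needs no prior data, so the reason given does not cover its absence.
- **Estimates usually appear in the report anyway.** This stands in part. Adverse-event frequency is a named variable, so frequencies will probably be shown. The SAP still commits to no effect measure or interval, which leaves the choice until after the data are seen.
- **An interval will not establish efficacy.** This stands. The study is non-randomized, and NR-C is drawn from patients who did not qualify or who declined (protocol, Study design). A narrow interval can still be biased.
- **The SAP does not say that non-significance will be read as no effect or equal safety.** Also true. The point is that nothing planned guards against that reading.

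A reader might also infer more than the documents support:

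- **That NR-RTX will be small, at 20–30% of enrolment.** The protocol's Background says "only 70-80% of the patients respond to the treatment (responders". That is a general figure, not tied to this study's four-week CAS rule, and a share of an unstated enrolment is not a group size. NR-C comes from a separate pool.
- **That the protocol's 2-point CAS improvement can serve as a margin, with no effect declared when the interval excludes 2 points.** That threshold classifies an individual's response to iv GC after four weeks; it is not a difference between group means. It makes little sense against R-GC, who were selected for having reached it. Such a rule would also misfire. In simulations with a true benefit of about 1 point (SD 1.5, percentile-bootstrap interval), it labelled about 35–37% of studies with 10 per group, and 46–48% with 20 per group, as showing no effect.

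**Conclusion.** The point holds for the CAS and adverse-event comparisons: as written, the plan yields p-values that cannot show how large an effect has been demonstrated or ruled out. It should be corrected, but it does not invalidate the design.

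The gap itself follows from the text and needs no assumption. Its numerical size does: the half-widths and power above rest on assumed group sizes, equal allocation, SD 1.0 to 2.0 and a conventional 5% level, which the SAP does not state. Text ahead of SAP section 1 was not available for this review.

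Two stronger conclusions should not be drawn. The documents do not show that the study is underpowered, because they give no sizes. Nor would an interval separate a drug that fails from a study with too few patients in any causal sense. It would separate a precise comparison from an imprecise one, with confounding still to be considered.

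**What to change.** Keep the tests in SAP section 3 and add:

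1. For each CAS comparison of NR-RTX with NR-C and with R-GC, report the difference in means with a Welch t-based 95% CI, optionally with the Mann-Whitney probability index and its CI. A percentile bootstrap is a poorer choice in small groups: in simulation its nominal 95% coverage was about 91% at 8 to 10 per group, against about 95% for a t interval.
2. For adverse events and other dichotomous variables, report the risk difference with a 95% CI by a small-sample method named in advance.
3. State that a non-significant p-value will not be reported as no effect or as equally safe, and that results will be interpreted from the range of the interval. Set no 2-point rule.
4. State that the intervals describe precision only, given the non-randomized groups and the origin of NR-C.

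Any precision figures added to section 1.4 should be labelled as illustrations over assumed sizes and SD 1.0 to 2.0, since no planned sizes exist.

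The cost is a few lines of SAP text and minor programming, with no added patients and no change to treatment. The conclusions will be more cautious. An interval may occasionally disagree with its test at the margin, which item 3 settles in favour of the interval.
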